8.9 Withdrawal of Informed Consent for Donated Biological Samples

If a patient withdraws consent to the use of voluntarily donated biological samples, then the samples will be disposed of/destroyed, and the action documented. If samples are already analyzed, Aprea Therapeutics AB is not obliged to destroy the results of this research. As collection of the genetic blood sample is a voluntary part of the study then the patient may continue in the study.

9.0 STATISTICS

At least 25 evaluable patients will be enrolled in the Main Study. Up to 25 patients will be enrolled in the Sub-Study.

9.1 Sample Size

The aim is to determine the preliminary efficacy of APR-246 with PLD. The endpoint of interest is the ORR as defined in Section 8.3.2.2.

A two stage design is used to test the null hypothesis that the true response rate of APR-246 in combination with PLD is $\leq 10\%$ versus the alternative that the true response rate is $\geq 30\%$. In the first stage, 16 patients will be assessed for response; if ≤ 1 response is seen in these 16 patients the study will be curtailed for futility. Otherwise the study will continue and a further 9 patients will be entered, for a total of 25 evaluable patients. If ≥ 5 responses are observed in these 25 patients, the null hypothesis will be rejected in favor of the alternative. This design provides 90.3% power and a 1-sided alpha of 9.5%.

Sub-Study Sample Size:

The aim is to determine the safety, tolerability and efficacy of a shorter infusion of APR-246 with PLD. The endpoint of interest is safety.

At one of the shorter infusion levels (3 hr 4.5 g, 4 hr 4.5 g, or 4 hr 3.7 g) if there are 0 or 1 out of 6 patients with DLTs across the first 6 patients, then an additional 8 patients will be treated for an initial total of N=14. If 0 or 1 out of 14 responses are seen, then recruitment will cease. If 2 or more out of 14 responses are seen, a further 11 patients will be recruited for a total of N=25. Observance of 5/25 responses will result in rejection of the null hypothesis. The design carries 89% power and a 1-sided type I error of 9.1% to test the null hypothesis that the true response rate is $\leq 10\%$ vs the alternative that the true response rate is 30%.

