
Criteria for Evaluation:
 
Efficacy:
 
Patients with measurable disease will be assessed using RECIST 1.1 criteria.
 
Safety:
 
AEs will be collected throughout the study, from informed consent until 30 days after the last administration of study treatment. AEs will be graded according to NCI CTCAE version 4.0. Serious adverse events (SAEs) will be reported according to Directive 2001/20/EC and 2005/28/EC and the International Conference on Harmonisation (ICH) Good Clinical Practice (GCP) guidelines.

Main Study Sample Size Calculation:
 
This study uses a two-stage design to test the null hypothesis is that the true response rate of APR-246 in combination with PLD is $\leq 10\%$ versus the alternative that the true response rate is $\geq 30\%$ in patients with platinum-resistant, TP53-mutated HGSOc. In the first stage, 16 patients will be assessed for response; if ≤ 1 response is seen in these 16 patients the study will be curtailed for futility. Otherwise the study will continue and a further 9 patients will be entered, for a total of 25 evaluable patients. If ≥ 5 responses are observed in these 25 patients, the null hypothesis will be rejected in favor of the alternative. This design provides 90.3% power and a 1-sided alpha of 9.5%.

Sub-Study Sample Size:
 
At one of the shorter infusion levels (3 hr 4.5 g, 4 hr 4.5 g, or 4 hr 3.7 g) if there are 0 or 1 out of 6 patients with DLTs across the first patients, then an additional 8 patients will be treated for an initial total of N=14. If 0 or 1 out of 14 responses are seen, then recruitment will cease. If 2 or more out of 14 responses are seen, a further 11 patients will be recruited for a total of N=25. Observance of 5/25 responses will result in rejection of the null hypothesis. The design carries 89% power and a 1-sided type I error of 9.1% to test the null hypothesis that the true response rate is $\leq 10\%$ vs the alternative that the true response rate is 30%.

LIST OF ABBREVIATIONS

AE	Adverse Event
ALP	Alkaline Phosphatase
ALT	Alanine Aminotransferase
AML	Acute Myeloid Leukemia
ANC	Absolute Neutrophil Count
APTT	Activated Partial Thromboplastin Time
AST	Aspartate Aminotransferase
AUC	Area Under the Curve
CA	Competent Authority
CA-125	Cancer Antigen 125
CD	Candidate Drug
CLL	Chronic Lymphocytic Leukemia
C _{max}	Maximal Plasma Concentration
CNS	Central Nervous System
CR	Complete Response
CT	Computed Tomography

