2.2 Disease Background

Ovarian cancer is the sixth most commonly diagnosed cancer among women in the world, at over 60,000 cases per year, and causes more deaths per year than any other cancer of the female reproductive system [6]. Ovarian cancer has been of considerable interest to clinical cancer investigators due to the fact that it is among the most chemosensitive of all solid tumors [7]. The commonest histological subtype is HGSOC, which is the focus of this study.

First line management of HGSOC involves optimal debulking surgery and platinum/taxane combination chemotherapy. Although this often produces a radiological complete response, the majority of patients will subsequently relapse and eventually develop platinum resistance to which the patient will ultimately succumb. The 5-year survival rate remains poor at less than 40%. Thus, there is a need for improved treatment of relapsed ovarian cancer.

Patients are generally retreated at relapse with platinum-based combinations unless the cancer relapses within 6 months of previous platinum-based chemotherapy (previously referred to as 'platinum resistant'). Patients who relapse within this timescale have poor prognosis and are often resistant to multiple chemotherapeutic agents [8]. Single-agent therapies used to treat this subset of patients include weekly paclitaxel, PLD and topotecan. The response rate is in the 10–15% range and overall survival is approximately 12 months [9].

HGSOC accounts for approximately 70% of epithelial ovarian carcinoma in Europe and North America [10]. Mutant TP53 is a hallmark of HGSOC, resulting in deregulation of cell cycle checkpoints and uncontrolled tumor cell proliferation and thus represents a key driver event. Pathogenic TP53 mutations have been quoted as occurring in up to 96% of patients with HGSOC [4].

APR-246 has been shown to induce apoptosis and cell death in cancer cells with mutant or otherwise non-functional p53, and in addition to display strong synergistic anticancer effects in combination with several conventional chemotherapeutic drugs including platinum drugs and doxorubicin [11, 12].

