8.3.3.3 Overall Response Rate

Best overall response, being confirmed and maintained for at least 28 days as defined in Section 8.3.2.2 and Table 7, will constitute the primary endpoint for response assessment and analysis.

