9.4.1 Efficacy Data

Overall Response Rate

Best overall response according to RECIST 1.1 will be presented along with the associated exact Clopper-Pearson 2-sided 95% and 1-sided lower 90% binomial confidence limits [20].

Progression-free Survival

PFS is defined as the time from registration to the time of disease progression or relapse (according to RECIST 1.1 only) or death. Patients who do not experience a PFS event will be censored at their last clinic visit contact for the assessment of disease progression.

PFS time will be summarized via a Kaplan-Meier curve with 95% confidence interval. Median PFS will be estimated from the Kaplan-Meier and presented long with 2-sided 95% confidence limits using the method of Brookmeyer and Crowley (1982) [21]. The PFS rate at 3, 6 and 9 months' follow-up will also be presented together with 2-sided 95% confidence limits using the method of Klein (2007) [22].

Evaluation of Biomarkers

The relationship between biomarkers and efficacy in terms of PFS and RECIST response will be explored using logistic regression methodology and accelerated failure time analysis.

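### Is the 10% null too low, given that the protocol puts single agents such as PLD at 10–15%?

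*Combined protocol and SAP*

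**What the plan says.** Section 9.1 sets a two-stage test for the Main Study. The null is a true response rate of at most 10% for APR-246 combined with PLD, and the alternative is at least 30%. The study stops if 0 or 1 of the first 16 patients respond. Otherwise it continues to 25, and with 5 or more responses "the null hypothesis will be rejected in favor of the alternative". The stated properties are: "This design provides 90.3% power and a 1-sided alpha of 9.5" per cent. The Sub-Study uses the same hypotheses with a first stage of 14, again stopping at 0 or 1, and 5/25 for rejection: "The design carries 89% power and a 1-sided type I error of 9.1" per cent.

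Section 2.2 names weekly paclitaxel, PLD and topotecan as single agents for this population and says: "The response rate is in the 10–15% range". Section 2.7 reports that topotecan, paclitaxel and PLD are similarly effective.

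The primary endpoint in Section 8.3.3.3 is strict: "Best overall response, being confirmed and maintained for at least 28 days". Section 9.4.1 will present the response rate with "exact Clopper-Pearson 2-sided 95% and 1-sided lower 90% binomial confidence limits". Section 9.2 leaves further detail on analysis and presentation to a SAP written before data lock.

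**The concern.** All patients in both cohorts receive PLD and nobody is randomised to PLD alone, so the only readable benchmark for the backbone is the 10–15% in Section 2.2. The null sits at the lowest point of that range. Section 9.1 gives the rejection probability only at 10%. If PLD alone gave 15% and APR-246 added nothing, the study would still be called positive nearly one time in three. The only reading attached to 5/25 is that it favours the alternative of at least 30%, and Section 9.4.1 does not name a value against which the 1-sided 90% limit is to be judged. The worry is that 5/25 or 6/25 could be reported as support for 30% when it is also compatible with a single-agent rate.

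**Working it through.** **Inputs.** Main Study: n1 = 16, stop at ≤ 1, total 25, reject at ≥ 5. Sub-Study: n1 = 14, same stopping and rejection counts (5/25 read as 5 or more). Null 10%, alternative 30% (all Section 9.1). Single-agent range 10–15% (Section 2.2). Limits: Clopper-Pearson (Section 9.4.1).

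**Formula.** With X1 the stage-1 responses and X2 the stage-2 responses, P(reject | p) = Σ over x ≥ 2 of P(X1 = x) × P(X2 ≥ 5 − x). For x ≥ 5 the second factor is 1.

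**Step 1: the plan's own figures (Main Study).**

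| Term | p = 10% | p = 30% |
|---|---|---|
| x = 2 | 0.2745 × 0.0530 = 0.0145 | 0.0732 × 0.5372 = 0.0393 |
| x = 3 | 0.1423 × 0.2252 = 0.0321 (unrounded factors) | 0.1465 × 0.8040 = 0.1178 |
| x = 4 | 0.0514 × 0.6126 = 0.0315 | 0.2040 × 0.9596 = 0.1958 |
| x ≥ 5 | 0.0170 | 0.5501 |
| Sum | 0.0951 | 0.9030 |

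These are the stated 9.5% and 90.3%. The same sum with n1 = 14 gives 0.0908 and 0.8906, the stated 9.1% and 89%.

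**Step 2: the same rule at other true rates.**

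| True rate | Main Study | Sub-Study |
|---|---|---|
| 8% | 4.4% | 4.2% |
| 10% | 9.5% | 9.1% |
| 12.5% | 19.0% | 18.2% |
| 15% | 31.0% | 29.9% |
| 30% | 90.3% | 89.1% |

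At 15% in the Main Study the terms are 0.0391 + 0.0915 + 0.1007 + 0.0791 = 0.3104.

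**Step 3: what the planned limits show, n = 25.** The 1-sided 90% lower limit for k responses is the 10% quantile of Beta(k, 26 − k).

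| Responses | Lower 90% limit | 2-sided 95% interval |
|---|---|---|
| 5 | 10.1% | 6.8–40.7% |
| 6 | 13.1% | 9.4–45.1% |
| 7 | 16.3% | 12.1–49.4% |

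At 5/25 the lower limit just clears 10%, so it agrees with the rejection rule at the stated null. The limits at 5/25 and 6/25 do not exclude 15%.

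**Step 4: what single results say about 15% against 30% (Main Study).** P(exactly 5) = P(≥ 5) − P(≥ 6), and likewise for 6.

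- Exactly 5/25: 0.3104 − 0.1603 = 15.0% at a true 15%; 0.9030 − 0.8042 = 9.9% at 30%.
- Exactly 6/25: 0.1603 − 0.0694 = 9.1% at 15%; 0.8042 − 0.6588 = 14.5% at 30%.

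Taken together the two counts have almost the same probability at either rate (24.1% and 24.4%), but only because they point in opposite directions: 5/25 leans modestly to 15% and 6/25 modestly to 30%.

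**Step 5: price of a formal reading against 15%.** The smallest count whose lower limit exceeds 15% is 7/25. The chance of reaching it is 65.9% at a true 30% (Sub-Study 65.6%) and 6.9% at 15% in either cohort. At 7/25 the 2-sided 95% interval still includes 15%.

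**The case for a change.** The strongest case for a change is that, without a control arm, a positive result will be compared with PLD alone whatever the formal null says. Section 2.7 gives no reason to place PLD at the bottom of the range. The study is open-label and the SAP need only precede data lock, so the interpretation could be settled after the responses are known. A few added figures and a reading rule would cost no patients and leave the test alone.

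Part of this stands. The rejection probabilities at 12.5% and 15% are correct, and 5/25 cannot be read as showing benefit over PLD. But the protocol makes no such claim: the hypothesis concerns the combination, and the aim is preliminary efficacy. Speaking of rejection in favour of the alternative is conventional wording for a two-stage test; it does not assert that the true rate is 30%. Printing the extra probabilities in Section 9.1 would be harmless, but it would alter no decision and no result.

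The reading rule is a real trade-off. It creates a second tier of success at 7/25 and ties it to a class-level figure. The documents do not show that 10–15% refers to confirmed response, to this population, or to PLD at the study's dose, so the applicable rate could lie on either side of the range. If it were 8%, the present rule would reject only 4.4% of the time.

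**Conclusion.** No change follows. The stated error rates are correct for the stated null, and 10% lies within the range the protocol cites, though at its lower end. Any two-stage rule rejects more often as the true rate rises above the null; rejections at 12.5% (19.0%) or 15% (31.0%) are correct rejections of a rate of at most 10%. Where to set the null within 10–15% for a 25-patient preliminary efficacy screen is a fair design choice.

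The planned exact limits already give the needed caution: a reader of 5/25 sees 10.1% and 6.8–40.7%, and a reader of 6/25 sees 13.1% and 9.4–45.1%, so 15% is visibly not excluded. Analysts can say so in the report without a rule in the plan. A mandatory bar at 15% would lower the chance of the favourable statement at a true 30% from 90.3% to 65.9%.

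The conclusion takes Section 2.2 as the only readable benchmark. Section 2.7.1 is redacted, so nothing is inferred about whether a further rationale for 10% exists.

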Appendix V: Actions Required in Cases of Increases in Liver Biochemistry and Evaluation of Hy’s
Law 84

CLINICAL STUDY SYNOPSIS

Name of Sponsor: Aprea Therapeutics AB [name]	Study Phase: Phase II
Name of Finished Product: APR-246, concentrate for solution for infusion	
Name of Active Ingredient: 2-(hydroxymethyl)-2-(methoxymethyl)-1-azabicyclo [2,2,2] octan-3-one	
Title of the Study: PiSARRO-R: p53 Suppressor Activation in Platinum-Resistant High Grade Serous Ovarian Cancer, a Phase II Study of Systemic Pegylated Liposomal Doxorubicin Chemotherapy With APR-246	
Investigators and Study Centers: Please see Study Operations Manual	
Publication (Reference): To be confirmed	
Clinical Phases: Phase II	
Study Design and Number of Patients: This study is an open-label, multicenter phase II study to evaluate the preliminary efficacy of APR-246 with systemic pegylated liposomal doxorubicin (PLD) chemotherapy in TP53-mutated high grade serous ovarian cancer (HGSOC) in patients with recurrent disease occurring between 4 weeks and 6 months after a preceding platinum-based treatment (platinum-resistant patients). Different APR-246 infusion times will be explored. The Main Study will assess the standard 6 hour APR-246 infusion whilst the Sub-Study will explore shorter infusions (3 or 4 hour). At least 25 evaluable patients will receive the standard 6 hour APR-246 infusion. Up to 25 additional patients may be enrolled in a Sub-Study exploring shorter APR-246 infusion durations (3 or 4 hours). The Sub-Study will start enrollment after at least 6 patients have received the standard 6 hour infusion in the Main Study. The Sub-Study will be conducted in parallel with the Main Study. A safety review committee (SRC) will evaluate the first 6 patients who receive the standard 6 hour infusion and the first 6 patients in the Sub-Study, to determine whether further patients can be lled and receive the same APR-246 infusion duration, at the same dose.	

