 11. Is taking any concurrent (or within 4 weeks prior to registration) anti-cancer therapy, immunotherapy, radiotherapy, biological, or ancillary anti-cancer therapy, or any therapy that is considered to be investigational (i.e., used for non-approved indications(s) and in the context of a research investigation). Supportive care measures are allowed. Palliative limited radiation therapy for pain reduction is allowed.

Test Product, Dose and Mode of Administration:

Main Study:

Patients will receive a fixed dose of 4.5 g APR-246 (1.5 g of the dose during first 45 minutes followed by 3 g of the dose during 5 hours 15 minutes) on Days 1 to 4 with PLD 40 mg/m² on Day 4. The PLD administration to be given on Day 4 only should commence 2 hours after the start of the APR-246 infusion. Similarly for the following 28-day cycles, APR-246 will be administered on Days 1 to 4 with the PLD infusion on Day 4 starting 2 hours after the start of the APR-246 infusion. In all cycles, APR-246 will be administered as a 6-hour infusion.

Test Product, Dose and Mode of Administration:

Sub-Study:
 
Starting within 28 days of registration, patients will receive a fixed dose of 4.5 g APR-246 in a 2-step infusion, starting with a loading dose given during first 45 minutes followed by slower infusion of the remainder of the dose, during 2 hours 15 minutes on Days 1 to 4, with PLD 40 mg/m² on Day 4. The PLD administration to be given on Day 4 only should commence 2 hours after the start of the APR-246 infusion.
 
Other infusion durations and doses that may be explored in the Sub-Study are 4 hour 4.5 g, or 4 hour 3.7 g.

Duration of Treatment:
 
Patients will receive 28-day cycles of PLD chemotherapy with APR-246. Patients may continue to receive APR-246 with PLD for as long as in the Investigator's opinion they are benefiting from treatment and in the absence of disease progression and unacceptable toxicity. After the tenth 28-day cycle, data from assessments conducted within each treatment cycle will no longer be collected, but patients may continue to receive treatment after confirmation from the sponsor.

Reference Therapy, Dose and Mode of Administration:
 
Not applicable

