1.5 Safety Review Committee

After the first six patients have been enrolled in the Main Study, and after the first six patients are enrolled in the Sub-Study, a Safety Review Committee (SRC) will evaluate the safety, tolerability and all other data concerning the action of APR-246 to determine should the study proceed to complete enrollment, or should an alternative dose and/or schedule be explored. The SRC will consist of:

- Medical Monitor (Theradex[®]), who will chair the committee, or delegate
- Principal Investigator or delegate from each investigational site
- Medical Monitor (Aprea Therapeutics AB) or delegate

The Study Pharmacokineticist, Project Managers and other technical experts may also be invited as appropriate. If required, a SRC Remit document will define the exact membership and who should be present for decisions to be made.

The decisions and decision-making of the SRC on dose and duration of APR-246 infusion will be documented and provided to the investigators prior to dosing any new patients.

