4.0 STUDY DESIGN

4.1 Overview of Study Design

This study is an open-label, multicenter phase II study to assess whether patients with platinum-resistant TP53-mutated HGSOC will benefit from treatment with APR-246 and PLD chemotherapy. At least 25 evaluable patients will be included in this study. Patients may continue to receive treatment for as long as they are benefiting from it.

Different APR-246 infusion times will be explored. The Main Study will assess the standard 6 hour APR-246 infusion whilst the Sub-Study will explore shorter infusions (3 or 4 hour).

All patients will have pre-screening IHC to determine p53 status and therefore eligibility. Archived sections from the original tumor sample will be reviewed by a gynecological pathologist to confirm the diagnosis of HGSOC and positive IHC staining for p53. Patients without positive p53 staining will not be included.

Patients will receive standard 6 hour APR-246 infusion (fixed dose of 4.5 g APR-246) and PLD chemotherapy. After evaluation of the first six patients with the standard 6 hour infusion, a subgroup of up to 25 additional patients will be given the APR-246 dose over a shorter infusion time in order to evaluate this dosing schedule according to the same criteria as in the main study. The sub-study will be conducted in parallel with the main study.

At follow-up visits after the end of treatment, radiological tumor assessments should be performed every 8 weeks until protocol-defined progression occurs. For patients with stable disease, follow-up will take place until disease progression or until death.

All scans for each individual patient should have the same modality (CT or MRI) but CT is preferred.

A safety review committee (SRC) will evaluate the first 6 patients who receive the standard 6 hour infusion and the first 6 patients in the sub-study, to determine whether further patients can be enrolled and receive the same APR-246 infusion duration, at the same dose.

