6.4.1 Sub-Study Doses and Infusion Times

[figure not shown]
Follow the flowchart for the Sub-Study (Figure 5), starting with 3 hr 4.5 g dose. Switch to 4 hr 4.5 g infusion or 4 hr 3.7 g infusion, as indicated, based on the occurrence of dose-limiting toxicities (DLTs).

DLTs include:

- Grade 4 thrombocytopenia lasting greater than 7 days
- Grade 4 neutropenia lasting greater than 7 days
- Other grade 4 hematological toxicities which last at least 5 days
- Grade 3 or 4 febrile neutropenia
- Grade 3 or greater non-hematological toxicities; these include grade 3 or greater diarrhea, nausea or vomiting despite adequate treatment which last greater than 3 days
- Patients who are unable to be dosed for more than 5 weeks from the planned start date of the next cycle due to toxicity

Please refer to Section 6.5 for dose modification procedures.

Figure 5. Sub-Study Flowchart

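### The Sub-Study's 89% power and 9.1% alpha hold only with all 25 patients at one infusion level, but 25 also reads as the cap for a Sub-Study that plans switches between levels

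*Combined protocol and SAP*

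**What the plan says.** **The test.** Section 9.1 and the synopsis place the Sub-Study response test "At one of the shorter infusion levels (3 hr 4.5 g, 4 hr 4.5 g, or 4 hr 3.7 g"). A level with 0 or 1 DLTs in its first 6 patients takes 8 more, which makes 14. Recruitment stops if 0 or 1 of the 14 respond. Otherwise: "If 2 or more out of 14 responses are seen, a further 11 patients will be recruited for a total of N=25". Five responses in 25 reject the null hypothesis of a 10% rate against 30%, with 89% power and 9.1% one-sided type I error.

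**The size.** Section 9.0: "Up to 25 patients will be enrolled in the Sub-Study". The synopsis (study design and number of patients): "Up to 25 additional patients may be enrolled in a Sub-Study exploring shorter APR-246 infusion durations (3 or 4 hours"). Section 4.1: "a subgroup of up to 25 additional patients will be given the APR-246 dose over a shorter infusion time".

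**The switches.** Section 6.4.1 starts at 3 hr 4.5 g and refers to the Figure 5 flowchart: "Switch to 4 hr 4.5 g infusion or 4 hr 3.7 g infusion, as indicated, based on the occurrence of dose-limiting toxicities (DLTs"). The synopsis adds: "Other infusion durations and doses that may be explored in the Sub-Study are 4 hour 4.5 g, or 4 hour 3.7 g". Section 1.5 has the safety review committee meet "after the first six patients are enrolled in the Sub-Study" and choose between completing enrollment and exploring an alternative dose or schedule.

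**The concern.** The response test needs 6 + 8 + 11 = 25 patients at a single level. The size statements give the whole Sub-Study up to 25, and the synopsis sentence covers 3 and 4 hour infusions together. Taken at face value, the test uses every place and leaves none for a level tried first and then abandoned. The DLT gate and the switching rule nevertheless expect that a level may be abandoned.

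After any such switch, the 25-patient test cannot be completed within a total cap of 25. The readable text gives no operating characteristics for a smaller number at the tested level. The synopsis lists overall response rate among the Sub-Study's primary endpoints, so the stated power belongs to a primary analysis. The risk is that an active shorter infusion is missed more often than the plan says.

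**Working it through.** **Inputs**
- Section 9.1: null rate 0.10, alternative 0.30, stage 1 size 14, stop at 1 or fewer responses, total 25, reject at 5 or more.
- Sections 9.0 and 4.1 and the synopsis: at most 25 patients in the Sub-Study.
- Assumptions: the 25 is a total cap; *k* places are used at abandoned levels; both boundaries stay as stated. The *k* values are not in the readable text.

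**Formula.** With N = 25 − *k* at the tested level, X₁ ~ Bin(14, p) and X₂ ~ Bin(N − 14, p):

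P(reject) = Σ over x = 2 to 14 of P(X₁ = x) × P(X₂ ≥ 5 − x)

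For x of 5 or more the second factor is 1. Power uses p = 0.30 and alpha uses p = 0.10.

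**Step 1: reproduce the plan (N = 25, 11 patients in stage 2, p = 0.30)**
- x = 2: 0.1134 × 0.6873 = 0.0779
- x = 3: 0.1943 × 0.8870 = 0.1724
- x = 4: 0.2290 × 0.9802 = 0.2245
- x ≥ 5: 0.4158
- Sum: 0.8906

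The same sum at p = 0.10 is 0.0908. The stated 89% and 9.1% are therefore right for 25 patients at one level.

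**Step 2: six places used earlier (N = 19, 5 patients in stage 2, p = 0.30)**
- x = 2: 0.1134 × 0.1631 = 0.0185
- x = 3: 0.1943 × 0.4718 = 0.0917
- x = 4: 0.2290 × 0.8319 = 0.1905
- x ≥ 5: 0.4158
- Sum: 0.7165

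At p = 0.10 the terms are 0.0022 + 0.0093 + 0.0143 + 0.0092 = 0.0350.

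Six is chosen because the DLT gate in Section 9.1 and the committee review in Section 1.5 both use six patients.

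**Step 3: other numbers of places left**

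| Places left at tested level | Places used earlier | Power at 30% | Alpha at 10% |
|---|---|---|---|
| 25 | 0 | 89.1% | 9.1% |
| 24 | 1 | 87.4% | 8.0% |
| 23 | 2 | 85.3% | 7.0% |
| 22 | 3 | 82.7% | 6.0% |
| 21 | 4 | 79.6% | 5.1% |
| 20 | 5 | 76.0% | 4.3% |
| 19 | 6 | 71.7% | 3.5% |
| 18 | 7 | 66.7% | 2.8% |
| 17 | 8 | 61.1% | 2.2% |
| 16 | 9 | 55.0% | 1.7% |
| 15 | 10 | 48.5% | 1.3% |
| 14 | 11 | 41.6% | 0.9% |

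If two abandoned levels each used six places, 25 − 12 = 13 would remain and the 14-patient first stage could not be filled.

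The type II error is 100 − 89.1 = 10.9% with 25 at the level and 100 − 71.7 = 28.3% with 19.

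**The case against.** **The flowchart may settle it.** Section 6.4.1 tells sites to follow Figure 5, which is not shown. It may fix the number treated at each level and who counts. This stands as a limit on the size of the effect: 19 and 13 places left are scenarios, not facts from the plan. A switch after a few early DLTs would use fewer places, and with 2 to 5 used the power is 85.3% to 76.0%. Even so, any place used under a total cap lowers power.

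**The 25 may be meant per level.** Section 9.1 ties its N = 25 to one level, and Section 4.1 speaks of a shorter infusion time in the singular. On that reading 89% and 9.1% are correct as they stand. But Section 9.0 and the synopsis read more naturally as a total, and they would then understate the Sub-Study's possible size. Either reading needs an edit.

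**Safety comes first.** Section 9.1 names safety as the Sub-Study's endpoint of interest, and the efficacy aim is preliminary. That limits the consequence. It does not remove it, because the same section sets a formal response test with stated power and alpha.

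**Stronger readings a reader might infer.** None of these is supported:
- That the power figure is miscalculated. It reproduces.
- That the Sub-Study's power simply is 71.7%. That needs exactly six places used, a total cap, and the threshold of 5 kept at 19 patients.
- That false positives rise. Alpha falls in every row of the table.
- That responses would be pooled across regimens. Section 9.1 builds its 14 from the 6 patients assessed for DLTs at a level plus 8 more, so patients from another level are naturally left out. A confirming sentence is enough.

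**Conclusion.** The point holds as an internal inconsistency that makes a stated power conditional. It is not an arithmetic error. The 89% and 9.1% apply only when no Sub-Study place has been used at another level. If 25 is a total cap and the boundaries are kept, power falls to somewhere between 87.4% (one place used) and 41.6% (eleven used), and below 14 places the design cannot be run. The case that best matches the protocol's own groups of six gives 71.7% power with 3.5% alpha.

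Confidence is high that the stated figures require all 25 at one level. It is moderate that the cap bites in practice, because Figure 5 is not shown. The documents give no DLT rates, so no overall power averaged over possible switches can be stated. This should be fixed, but it does not undermine the test on the path where the first level is kept.

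**What to change.** Reconcile Section 9.0, Section 4.1 and the synopsis design paragraph with the Sub-Study sample size text in Section 9.1 and the synopsis. Check the result against Figure 5.

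- **If 25 is a total cap:** state that 89% and 9.1% apply only when all 25 patients are at one level. Give the lower power and alpha for smaller remaining numbers, as in the table. Confirm that only patients at the tested level count in the 14 and the 25. Say that with fewer than 14 places left the response results are descriptive.
- **If 25 is per tested level:** say so and correct the Sub-Study maximum. For illustration, six patients at one abandoned level would make it 6 + 25 = 31, and six at each of two would make it 12 + 25 = 37.

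No new stopping or rejection boundary is proposed.

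The change belongs in the protocol. Section 9.2 requires the SAP only before data lock, whereas the cap and the stage 1 decision operate during enrollment.

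The cost is wording, a short table and a lower stated power on the capped paths. A total cap needs no extra patients. A per-level reading means acknowledging a larger possible Sub-Study.
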